### 5.2. Adjustments for Covariates

The repeated measures models will include the fixed, categorical effects of treatment, visit (categorical covariate), treatment-by-visit interaction, as well as the continuous, fixed covariate of baseline, baseline-by-visit interaction, and age at baseline.

When an ANCOVA model is used to analyze a continuous efficacy or safety variable, the model will contain the main effects of treatment and appropriate baseline value and age at baseline included as covariates.

### **5.3. Handling of Dropouts or Missing Data**

#### **5.3.1. Handling Missing Data from Subject Dropouts**

A likelihood-based mixed effects model for repeated measures will be used to handle missing data. The model parameters are simultaneously estimated using restricted likelihood estimation incorporating all of the observed data. Estimates have been shown to be unbiased when the missing data are missing at random and when there is ignorable non-random missing data.

#### **5.3.2. Handling Missing Items in Calculating Totals**

All total and subscale scores for safety, efficacy, and health outcomes measures will be derived from individual items. If any of the individual items are missing or unknown, every effort will be made to obtain the score for the missing item or items.

For ADAS-Cog13 and ADCS-iADL, if >30% of the items are missing, the total score at that visit will be considered missing. If <30% of the items are missing, the total score will be imputed by prorating the nonmissing items. The imputed number will be rounded up to the nearest integer. For example, if the first item of ADAS-Cog13, “Word-Recall Task,” which ranges from a score of 0 through 10 (maximum = 10) is missing, and the second item “Commands,” which ranges from a score of 0-5 (maximum = 5) is missing, then the multiplication factor =  $85 / (85 - [10 + 5]) = 85 / 70 = 1.21$  (85 is the total score for the ADAS-Cog13). Thus, the total score for this example will be the sum of the remaining 11 items multiplied by 1.21.

For all other scales, if any item is missing, any total or sum involving that item will be considered missing.

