9.1.2. Secondary Efficacy Assessments

Alzheimer's Disease Assessment Scale—Cognitive subscale (ADAS-Cog; Rosen et al. 1984). The ADAS is a rater-administered instrument that was designed to assess the severity of the dysfunction in the cognitive and noncognitive behaviors characteristic of persons with AD. The cognitive subscale of the ADAS, the ADAS-Cog₁₃, consists of 13 items assessing areas of cognitive function most typically impaired in AD, for example, orientation, verbal memory, language, praxis, delayed free recall, and digit cancellation measures (Mohs et al. 1997). The ADAS-Cog₁₃ scale ranges from 0 to 85, with higher scores indicating greater disease severity.

Alzheimer's Disease Cooperative Study—Activities of Daily Living Inventory (ADCS-ADL; Galasko et al. 1997, 2004). The ADCS-ADL is a 23-item inventory developed as a rateradministered questionnaire that is to be answered by the patient's study partner. The ADCS-ADL subset of items (items 7 to 23) for instrumental activities of daily living (ADCS-iADL) will be used as a secondary efficacy measure. The focus in the mild AD dementia population is on

the instrumental activities of daily living (iADL) rather than the basic activities of daily living (bADL), which are thought to be affected in more severe stages of the disease. The range for the iADL score is 0 to 56, with lower scores indicating greater disease severity. For each of the specific items, the study partner is first asked if the patient attempted the ADL during the past 4 weeks. If the patient did attempt the ADL, the study partner is asked to rate the patient's performance level based on a set of performance descriptions. Scores for each item and the overall score for the tool are calculated. The range for the total ADCS-ADL score is 0 to 78.

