Integrated Alzheimer's Disease Rating Scale (iADRS). The iADRS comprises scores from the ADAS-Cog and the ADCS-iADL, 2 well-accepted measures in AD research. The iADRS is calculated as a linear combination of the total scores of the ADAS-Cog₁₃ (score range 0 to 85 with higher scores reflecting worse performance) and the ADCS-iADL (score range 0 to 56 with higher scores reflecting better performance). To account for the opposite directionality of the scores, the ADAS-Cog score is multiplied by (-1) in the calculation of the integrated scale. Then a constant (85) is added to anchor the ADAS-Cog at 0. The iADRS score is then calculated by summing the transformed ADAS-Cog₁₃ and the ADCS-iADL, as shown below:

iADRS score = $[-1(ADAS-Cog_{13})+85]+iADL$

The iADRS score ranges from 0 to 141 with lower scores indicating worse performance (Wessels et al. 2015).

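### Read literally, the SAP's instruction to round prorated ADAS-Cog13 and ADCS-iADL totals up adds about 0.4 to 0.5 point to each imputed total

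*SAP*

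**What the plan says.** SAP 5.3.2 (Handling Missing Items in Calculating Totals) covers two scales, ADAS-Cog13 and ADCS-iADL. When fewer than 30% of items are missing, "the total score will be imputed by prorating the nonmissing items". The next sentence reads: "The imputed number will be rounded up to the nearest integer".

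The worked example takes two missing ADAS-Cog13 items with maxima 10 and 5. It gives the factor as "85 / (85 - [10 + 5]) = 85 / 70 = 1.21" and obtains the total as "the sum of the remaining 11 items multiplied by 1.21".

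The two scales run in opposite directions. In Protocol 9.1.2 the ADAS-Cog13 "scale ranges from 0 to 85, with higher scores indicating greater disease severity". For the other scale, "The range for the iADL score is 0 to 56, with lower scores indicating greater disease severity". The iADRS subtracts ADAS-Cog13 and adds ADCS-iADL.

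Protocol 10.3.1 leaves the ADAS-Cog13 imputation algorithm to the SAP, so SAP 5.3.2 is the operative text. No other section changes the rounding rule. SAP 5.11.2 analyses the change from baseline in all three scores by MMRM, at a 1-sided alpha of 0.10.

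**The concern.** Proration estimates the full-scale total by scaling the observed sum. If the result is then always moved up to the next whole number, the estimate is never too low and is usually too high. A programmer who follows the sentence word for word would code a ceiling function.

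When an imputed follow-up total is paired with a complete baseline, the change score carries the whole shift. It looks like extra decline on ADAS-Cog13 and like retained function on ADCS-iADL. If item-level missingness differed between arms, part of the shift would pass into the secondary comparisons. The MMRM treats these changes as continuous, so the model does not need an integer.

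**Working it through.** **Inputs.** ADAS-Cog13 maximum 85 and missing maxima 10 + 5 (SAP 5.3.2); ADCS-iADL maximum 56 (Protocol 9.1.2). Assumed, because the documents do not give them: whole-number item scores, observed sums S spread evenly over the stated ranges, and one missing ADCS-iADL item with a maximum of 3 or 4.

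**The plan's own figure.** 85 / (85 − 15) = 85/70 = 1.2142857, which is 1.21 to two decimals. The printed factor is reproduced.

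**Error of a rule** = imputed total − exact prorated total, averaged over S.

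*Step 1: ceiling with the exact factor.* The factor 85/70 reduces to 17/14, so over 14 consecutive sums the amount added by the ceiling takes the values 0, 1/14, …, 13/14. The mean is 13/28 = 0.46. Counting over S = 10 to 50 gives +0.47: 38 of 41 totals (93%) are too high and none is too low. For example, S = 25 gives 30.36, which becomes 31.

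*Step 2: the two-decimal factor alone.* (1.21 − 1.2142857) × S = −0.0043 × S. This is −0.04 at S = 10, −0.11 at S = 25 and −0.30 at S = 70. It lowers the score.

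*Step 3: both together, as the example reads literally.* Ceiling of 1.21 × S, S = 10 to 50: mean +0.38, single errors from −0.14 to +0.86.

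*Step 4: ADCS-iADL, ceiling with the exact factor.* With 3 points missing the factor is 56/53 = 1.0566, and the mean is +0.41 (S = 25 to 53). With 4 points missing it is 56/52 = 1.0769, and the mean is +0.43 (S = 25 to 52).

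*Step 5: conventional rounding with the exact factor, halves up.*

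| Case | Ceiling | Nearest integer |
|---|---|---|
| ADAS-Cog13, 15 points missing, S 10–50 | +0.47 | +0.03 |
| ADCS-iADL, 3 points missing, S 25–53 | +0.41 | +0.03 |
| ADCS-iADL, 4 points missing, S 25–52 | +0.43 | +0.00 |

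With no integer rounding and the exact factor, the error is zero.

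*Step 6: effect on a treatment contrast.* Take a shift of 0.5 point per imputed follow-up visit and complete baselines. The contrast then moves by 0.5 × (difference in imputation rates). The rates are assumed; the documents give none.

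| Rates by arm | Shift in contrast (points) |
|---|---|
| equal | 0 |
| 5% v 2% | 0.5 × 0.03 = 0.015 |
| 10% v 5% | 0.5 × 0.05 = 0.025 |
| 20% v 10% | 0.5 × 0.10 = 0.05 |

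*Step 7: iADRS.* If both scales are imputed at a visit, the shifts nearly cancel: −0.47 + 0.41 = −0.06, or −0.47 + 0.43 = −0.04. If only one is imputed, its full shift remains.

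**The case against.** The strongest reply is that the sentence is loose wording. It combines rounding up with the nearest integer, and the latter normally means conventional rounding. On that reading the half-point bias is gone, and using 1.21 would leave about −0.10 point in the example (S = 10 to 40). This may well be the intention. It does not remove the point, because two programmers could build different data from the same text.

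Three stronger readings are tempting, and the documents do not support them.

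- A reader might infer that the shortened factor adds to the upward bias. In the SAP's example it does the opposite: 1.21 is below 85/70 and offsets part of the ceiling. The factor is also correctly rounded as printed, so the division itself contains no error.
- A reader might apply two-decimal factors to ADCS-iADL (1.06 and 1.08) and obtain +0.59 to +0.61. The SAP shows two decimals in one ADAS-Cog13 illustration and states no general rule. Only the exact-factor figures can be attributed to it.
- A reader might infer that the treatment comparisons are biased. The rule is the same in every arm of a blinded trial, and nothing in the documents suggests that item missingness differs by arm. SAP 5.3.2 also asks sites to try to recover missing items first. If baseline and follow-up are both imputed, the shifts largely cancel in the change.

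Whole-number imputed totals do sit on the same grid as observed totals. Rounding to the nearest integer keeps that advantage without the shift.

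**Conclusion.** Wrong as written, at the lowest severity. The rounding sentence, taken at its word, biases imputed totals upward by about 0.4 to 0.5 point with the exact factor; the literal ADAS-Cog13 example nets slightly less because of its shortened factor. These averages rest on the assumed spread of observed sums and, for ADCS-iADL, on assumed item maxima, so they vary somewhat with the pattern of missing items.

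The practical effect is very small. It is confined to imputed visits on the secondary scales and does not reach the primary tau-PET analysis. Any movement in a treatment contrast depends on unequal imputation rates and is at most a few hundredths of a point at the assumed rates, on scales of 85 and 56 points. The case for changing the text is that the bias is systematic, the wording is ambiguous, and the correction has no statistical cost.

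**What to change.** In SAP 5.3.2, replace the rounding sentence with one stating that the prorated total is used unrounded. If whole numbers are wanted, state that it is rounded to the nearest integer and say how halves are treated. Write the example's factor as 85/70 and state that factors are carried at full precision for both scales.

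The cost is one line of SAP text and one line of code. If the totals have already been derived, the clinical study report should state which rounding and which factor precision were used.

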### **5.4. Multicenter Studies**

This study will be conducted by multiple investigators at multiple sites internationally. A listing including country, investigator site with address, number of subjects enrolled (randomized) by each site and unique subject IDs will be presented.

### **5.5. Multiple Comparisons/Multiplicity**

No adjustments will be made for multiple comparisons.

### **5.6. Population for Analysis**

The Efficacy population is defined as all randomized participants who take at least 1 dose of double-blind study treatment and have at least 1 postdose efficacy measurement, which is used to assess the effectiveness of the study drug regimen; all observed data will be included (including data gathered after a subject discontinues study drug).

In order to assess the study drug treatment effect, data gathered after a subject discontinues study drug will not be included in the analysis of per protocol population.

Additionally, when change from baseline is assessed, subjects will be included in the analysis only if both a baseline and at least 1 valid post-baseline measure are available.

All subjects who received at least 1 dose of randomized study treatment (LY3202626 or placebo) will be included in the safety analysis set. If an LY3202626 dose group is dropped following an interim analysis, subjects switched to the remaining LY3202626 dose and remaining on treatment will be accounted for as a separate group.

For the Lumbar Puncture addendum, the analysis sets will include all those subjects whose eligibility was determined by the respective biomarker, who signed consent for addendum, and who have a baseline and at least 1 valid post-baseline cerebrospinal fluid (CSF) assessment.

The PK analysis set is defined as all subjects in the safety population who have at least 1 post-dose PK assessment. The population PK analyses will be performed using this analysis set.

The primary and secondary efficacy measures will be analyzed using the efficacy population unless otherwise specified. In addition, the primary measure will be analyzed using per-protocol populations to verify the robustness of the results. Summaries and analyses for safety measures will be based on the safety population.

[Table LLCF.SAP.1](#) below defines each of the analysis populations used in this study.

[Table LLCF.SAP.2](#) lists the study measures that will be summarized and/or analyzed for each population.

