Patients who discontinue study treatment early should receive all early discontinuation procedures as described in Section 2. Patients should be encouraged to remain in the study until Week 52 (Visit 18), even if study treatment has been discontinued, and they should continue to participate in scheduled visits as described in Section 2. Patients who agree to remain in the study after discontinuing study treatment should continue to participate in scheduled visits and assessments, as appropriate, with the exception of PK measurements and PET scans, after completing the early discontinuation assessments described in Section 2, as appropriate. The follow-up visit (Week 56) is not required for patients who discontinue study treatment early and continue in the study, unless the study drug was discontinued within that last 4 weeks of the study. The Lilly-designated medical monitor may be consulted regarding the details of managing a specific patient who discontinues treatment but remains in the study.

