9.6. Pharmacodynamics

The peripheral dose-dependent PD activity of LY3202626 and placebo administration will be evaluated by analysis of plasma $A\beta_{1-40}$, $A\beta_{1-42}$, $A\beta_{1-x}$ as measured using validated immunoassays. These plasma based biomarkers will provide an assessment of target engagement and the data will inform dose optimization. Central PD will be assessed in a substudy in which CSF is collected from participating patients.

Biological samples collected to measure PD parameters will be identified by the patient number (coded) and retained for a maximum of 15 years following last patient visit for the study at a facility selected by Lilly or its designee.

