10.3. Statistical Analyses

10.3.1. General Statistical Considerations

Statistical analysis of this study will be the responsibility of Eli Lilly and Company.

Unless otherwise specified, all safety analyses will be conducted on the safety population and all efficacy and PD analyses will be conducted on the efficacy population as defined above (Table LLCF.3).

No adjustments will be made for multiple comparisons.

All total and subscale scores will be derived from individual items. If any individual item is missing, the corresponding total and subscale scores will be considered missing, except for the ADAS-Cog₁₃, which will be imputed. The imputation algorithm will be specified in the statistical analysis plan (SAP).

All tests of treatment effects of biological efficacy or clinical efficacy will be conducted at a 1-sided α =.10, unless otherwise stated. Safety assessments will be conducted at a 2-sided α =.05.

A repeated measures analysis refers to a restricted maximum likelihood (REML)-based, mixed effects repeated measures analysis using all the longitudinal observations at each post-baseline

visit. A repeated measures analysis model will include the fixed, categorical effects of treatment group, visit, and treatment-by-visit interaction, as well as the continuous, fixed covariates of baseline and the baseline-by-visit interaction, unless otherwise noted. Unless otherwise specified, when an ANOVA model is used to analyze a continuous efficacy variable, the model will contain the main effects of treatment. Similar logic is applied to an ANCOVA model, which in general, refers to the ANOVA model with baseline value added as a covariate. Type III sum-of-squares for the least squares (LS) LS Means will be used for statistical comparisons using an ANOVA or ANCOVA. Categorical comparisons between treatment groups will be performed using Fisher's exact tests, where appropriate.

Any change to the data analysis methods described in the protocol will require an amendment to the protocol only if it changes a principal feature of the protocol. Any other change to the data analysis methods described in the protocol, and the justification for making the change, will be described in the clinical study report (CSR). Additional exploratory analyses of the data will be conducted as deemed appropriate.

SAS® software will be used to perform most or all statistical analyses.

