**Table LLCF.SAP.2. Efficacy and Safety Measures Summarized and/or Analyzed for Each Analysis Population**

Population Name	Variables Assessed
Enrolled	Listings
Efficacy	Tables, Listings and/or Figures of the following: subject disposition, subject characteristics, pre-existing conditions, significant historical diagnoses ADAS-Cog 13 , ADCS-iADL (and factor analyses), NPI, FAQ, ECog, BASQID, MoCA, MMSE, plasma A $\beta$ parameters, vMRI parameters, CSF parameters, AV-45 and Tau PET parameters and concomitant medications.
Safety Population	Tables, Listings and/or Figures of the following: Compliance, adverse events, laboratory results, vital signs, weight, ECG, MRI, skin examination, eye examination, and C-SSRS.
Per-Protocol Population	Tables, Listings and/or Figures of 18F-AV-1451 PET SUVr.

Abbreviations: ADAS-Cog13 = 13-item Alzheimer's Disease Assessment Scale – Cognitive subscale; ADCS-iADL = Alzheimer's Disease Cooperative Study-Activities of Daily Living inventory; BASQID = Bath Assessment of Subjective Quality of Life in Dementia; CSF = cerebrospinal fluid, C-SSRS = Columbia-Suicide Severity Rating Scale; ECG = electrocardiogram; ECog = Everyday Cognition; FAQ = Functional Activities Questionnaire; MMSE = Mini-Mental State Examination; MoCA = Montreal Cognitive Assessment; MRI = magnetic resonance imaging; NPI = Neuropsychiatric Inventory; PET = positron emission tomography; SUVr = standardized uptake value ratio.

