## 5.12. Bioanalytical and Pharmacokinetic/Pharmacodynamic Methods

### 5.12.1. Analysis of Plasma A $\beta$

To evaluate the change in plasma A $\beta$  analytes (including assayed plasma A $\beta_{1-40}$ , A $\beta_{1-42}$ , A $\beta_{1-x}$  after treatment, an MMRM will be used to compare percent change from baseline to week 52. Log transformation will be applied to data prior to analysis and result will be back-transformed to get percent change from baseline.

The model for the fixed effects will include terms for the following independent effects: log-transformed baseline plasma A $\beta$ , treatment, visit, treatment-by-visit interaction. The dependent variable is the change from baseline in log transformed plasma A $\beta$  analytes. Visit will be considered a categorical variable with values equal to the visit numbers at which plasma A $\beta$  is assessed. A similar MMRM analysis will be performed on untransformed percent change from baseline in plasma A $\beta$  analytes if the residual analysis suggests the log transformed analysis is inappropriate.

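### The Week 52 plasma Aβ comparison mixes on-drug and off-drug samples, and no on-treatment analysis is planned for a measure meant to show target engagement

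*SAP*

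**What the plan says.** **Population and data rule.** Protocol 10.3.1 states that, unless otherwise specified, "all efficacy and PD analyses will be conducted on the efficacy population as defined above". SAP Table LLCF.SAP.2 agrees: its Efficacy row includes "plasma A $\beta$ parameters, vMRI parameters, CSF parameters, AV-45 and Tau PET parameters and concomitant medications". For that population SAP 5.6 says "all observed data will be included (including data gathered after a subject discontinues study drug".

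**Model.** Under SAP 5.12.1, "an MMRM will be used to compare percent change from baseline to week 52". The model works on log change, has visit and treatment-by-visit terms, and is back-transformed. It has no on-treatment restriction.

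**Where off-drug data are removed.** SAP 5.6 says that, to assess the effect of the study drug, "data gathered after a subject discontinues study drug will not be included in the analysis of per protocol population". Table LLCF.SAP.2 limits the per-protocol population to "Tables, Listings and/or Figures of 18F-AV-1451 PET SUVr".

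**Sampling after stopping drug.** Protocol 8.1.1 encourages these patients to stay to Week 52; they "should continue to participate in scheduled visits and assessments, as appropriate, with the exception of PK measurements and PET scans". Plasma PD is not among the exceptions.

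**Purpose.** Protocol 9.6: "These plasma based biomarkers will provide an assessment of target engagement and the data will inform dose optimization".

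**The concern.** Whether a dose engages its target is a question about patients who are taking it. A sample drawn after drug has been stopped, once Aβ has moved back toward baseline, says nothing about what the dose does. Averaged in, it pulls the apparent reduction toward zero in both LY3202626 arms, while stopping placebo should change nothing.

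Plasma Aβ is part of a secondary objective. SAP 5.12.2 has reduced the CSF biomarkers to listings because few patients joined the addendum, so plasma Aβ is the Aβ measure that still has a planned comparison between arms. If its Week 52 estimate is read as on-drug engagement, each dose will look weaker than it is in patients still taking it.

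The SAP recognises the distinction but applies it where it does little. Off-drug data are removed only for tau PET, and PET is not repeated in these patients once the early discontinuation assessments are done. They are kept for plasma Aβ, where sampling goes on.

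**Working it through.** **1. The plan's own figures.** Protocol 5.2 gives about 380 randomized, about 320 completers and about 15% drop-out.
- 320 / (1 − 0.15) = 376.5, or 377, against 380.
- 380 × 0.85 = 323, against 320.
- The arms in Protocol 5.1 give 2 × 167 + 45 = 379.

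These agree within rounding, but they are enrolment figures. The documents give no plasma Aβ effect and no share of samples taken off drug.

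**2. Which samples can be off drug.** The Schedule of Activities places post-baseline plasma Aβ at Visits 5, 6, 7, 8, 9, 11 and 18 and at early discontinuation (ED).

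| Sample | What the footnotes say | Off drug in patients who stop but stay? |
|---|---|---|
| Visits 5–11 | c: assessments continue except PK and PET. j: PK samples not needed after stopping drug. n: PD sample taken when PK is taken | Unclear; c, j and n must be reconciled |
| Visit 18 | n: PD sample taken with the clinical laboratory samples | Yes, it is still due |
| ED | Scheduled, at no stated interval from last dose | Possibly; SAP 5.12.1 does not say whether it enters the model |

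For the clinical scales, SAP 5.11.2 says how ED visits that do not match the schedule are handled. SAP 5.12.1 has no such rule.

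Separately, Protocol 8.1.2 allows temporary suspensions, normally up to 4 weeks. Footnote j does not clearly cover them.

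**3. Effect on the Week 52 estimate.** Let R be the on-drug reduction, f the off-drug share of Week 52 samples in the arm, and r the fraction of the log change undone by the time of the off-drug sample. On the SAP's log scale:

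mean log change = (1 − f) ln(1 − R) + f (1 − r) ln(1 − R) = (1 − f r) ln(1 − R)

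apparent reduction = 1 − (1 − R)^(1 − f r)

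Inputs:
- R = 70% (3 mg) and 90% (12 mg). These are the CSF projections (Protocol 3.2 and 5.5), used as stand-ins because no plasma figure is given.
- f and r are assumptions. Placebo is assumed not to shift.

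Example: R = 0.90, f = 0.15, r = 1 gives 1 − 0.10^0.85 = 1 − 0.141 = 85.9%.

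| f | 90%, full recovery | 90%, half recovery | 70%, full recovery | 70%, half recovery |
|---|---|---|---|---|
| 0% | 90.0% | 90.0% | 70.0% | 70.0% |
| 5% | 88.8% | 89.4% | 68.1% | 69.1% |
| 15% | 85.9% | 88.1% | 64.1% | 67.2% |
| 30% | 80.0% | 85.9% | 56.9% | 64.1% |

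From f = 5% to 30% the shortfall under full recovery is 1.2 to 10.0 points for a 90% reduction and 1.9 to 13.1 points for a 70% reduction. Under half recovery it is 0.6 to 4.1 and 0.9 to 5.9 points. The direction is the same in every case with f and r above zero.

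**The case against.** The best defence is that SAP 5.1 adopts an intent-to-treat principle for all analyses unless otherwise specified. As an effect of assignment, the all-data estimate is not biased by off-drug samples. That stands, and it is why the all-data analysis should be kept. It does not answer the engagement question in Protocol 9.6.

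Four stronger readings are tempting, and the documents do not support them.

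- **That the effect of each dose is understated throughout.** Only Visit 18 is clearly sampled off drug. The model estimates each visit separately, so off-drug Visit 18 samples do not directly dilute the means at Weeks 2 to 24.
- **That 15% or 30% of Week 52 samples will be off drug.** Those percentages also appear in the protocol, but there they are study drop-out rates. Patients who leave the study give no Visit 18 sample. The relevant group is patients off drug but still followed, and it may be much smaller.
- **That confidence intervals will be wider by a known factor.** This needs an on-drug SD of log change, which the documents do not give.
- **That many early on-drug samples are lost because the Efficacy population requires a post-dose efficacy measurement.** The scales are first due at Week 24 or ED. A loss needs a patient who leaves before Week 24 and also misses the ED scales, and it depends on whether plasma Aβ itself counts as an efficacy measurement, which the SAP leaves open.

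Two further points count for the plan. SAP section 3 says most subjects would lack a Week 52 observation after early termination. It says so of the imaging biomarkers, but the Week 52 plasma contrast is likely to be thin too; that also makes the silence on ED samples matter more. And Protocol 10.3.5 allows modelling of plasma Aβ, which could address exposure, but only if judged appropriate.

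**Conclusion.** The point holds for Week 52. As planned, the plasma Aβ comparison at that visit estimates a treatment-policy effect, and it will understate on-drug target engagement to the extent that patients off drug but still followed give samples and their Aβ has recovered. No planned MMRM isolates the on-drug effect.

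The direction follows from the documents plus one assumption, that Aβ moves back toward baseline after stopping. The size does not: the off-drug share, the recovery and the plasma reduction are all unstated, so the tabulated figures illustrate and do not predict. At a 5% off-drug share the shortfall is at most 1.2 points (90% reduction) or 1.9 points (70% reduction), and with no off-drug samples it is nil.

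This is a worthwhile, inexpensive improvement. It does not show that the plasma analysis is invalid or that the earlier visits are affected.

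**What to change.** In SAP 5.6, Table LLCF.SAP.2 and 5.12.1:

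1. Define a PD analysis set parallel to the PK set: Safety-population patients with a baseline and at least one post-dose plasma Aβ sample. Protocol 10.3.1 leaves room for another set to be specified.
2. Pre-specify an on-treatment plasma Aβ MMRM as the target-engagement estimate. Exclude samples taken after permanent discontinuation or during a documented suspension.
3. State how ED samples enter: which visit they map to, and how close to the last dose they must be to count as on treatment.
4. Keep the all-data MMRM beside it as the treatment-policy estimate.
5. Report the number of off-drug samples by arm and visit, so the reader can see how much mixing occurred.

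Separately, reconcile footnotes c, j and n of the Schedule of Activities on PD sampling after drug is stopped.

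**Cost.** SAP wording, one date filter and one extra table, with no new data collection: Protocol 7.6 requires drug administration to be recorded, and 8.1.2 requires suspensions and restarts to be documented. The downside is somewhat fewer late samples and an estimate that describes only patients still taking drug.
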